**TRILUMINATE Pivotal CIP**  
(Version F)

Echocardiogram positive for IE (TEE recommended for patients with prosthetic valves, rated at least possible IE by clinical criteria, or complicated IE [paravalvular abscess]; TTE as first test in other patients) defined as follows: oscillating intracardiac mass on valve or supporting structures, in the path of regurgitant jets, or on implanted material in the absence of an alternative anatomic explanation; abscess; or new partial dehiscence of prosthetic valve or new valvular regurgitation (worsening or changing or pre-existing murmur not sufficient)

**Minor Criteria**

Predisposition, predisposing heart condition, or IDU

Fever, temperature >38°C

Vascular phenomena, major arterial emboli, septic pulmonary infarcts, mycotic aneurysm, intracranial hemorrhage, conjunctival hemorrhages, and Janeway lesions

Immunological phenomena: glomerulonephritis, Osler nodes, Roth spots, and rheumatoid factor

Microbiological evidence: positive blood culture but does not meet a major criterion as noted above (excludes single positive cultures for coagulase-negative staphylococci and organisms that do not cause endocarditis) or serological evidence of active infection with organism consistent with IE

**ETIOLOGY OF TRICUSPID REGURGITATION**

Will be determined as Degenerative, Functional, or Lead-Induced.

- **Degenerative Tricuspid Regurgitation**  
Tricuspid regurgitation primarily due to abnormality of the tricuspid apparatus

## TRILUMINATE Pivotal CIP (Version F)

- **Functional Tricuspid Regurgitation**  
Global or regional right ventricular wall motion abnormalities causing leaflet restriction or tethering with or without dilatation of the tricuspid annulus, but with no significant abnormalities of the tricuspid leaflets
- **Lead-Induced Tricuspid Regurgitation**  
ICD or pacemaker trans-tricuspid lead directly interfering with leaflet coaptation.

### **GAMMA-GT/GAMMA-GLUTAMYL TRANSFERASE (GGT)**

GGT is an enzyme that is found in many organs throughout the body, with the highest concentrations found in the liver. GGT is elevated in the blood in most diseases that cause damage to the liver.

### **GASTROINTESTINAL COMPLICATIONS**

Complications as a result of the TriClip™ procedure affecting the gastrointestinal tract requiring surgery. May include fecal impaction, bowel obstruction, etc.

### **HOSPITALIZATION (ALL-CAUSE)**

Defined as admission to inpatient unit or ward in the hospital for at least 24 hours, including emergency department stay. Excludes hospitalizations planned for pre-existing conditions, unless there is worsening in the baseline condition.

### **HEART FAILURE (HF) HOSPITALIZATION**

Defined as an event that meets the following criteria:

- 1) Hospitalization ( $\geq 24$  hours) with the primary reason for admission as acute decompensated HF and administration of intravenous or mechanical heart failure therapies, especially IV administration of diuretic therapy
- 2) An unscheduled or unplanned admission to the emergency department, hospital outpatient observation unit, or hospital inpatient unit, and IV administration of diuretic therapy.
- 3) Subject arrives in emergency department with clinical presentation meeting the criteria of heart failure, but dies in the emergency department before hospital admission.

Overnight stays at nursing home facilities, physical rehab or extended care facilities, including hospice, will be included in the definition of hospitalization if related to a heart failure event. Elective heart failure “tune-ups” that occur following the TriClip™ procedure and prolong the Index hospitalization will not count as a heart failure hospitalization.

### **OTHER CARDIOVASCULAR HOSPITALIZATION**

Study Document No: ABT-CIP-10249

Study Name: TRILUMINATE Pivotal

**CONFIDENTIAL:** May not be reproduced outside of Abbott without written permission from Document Control. This is a quality record which will be retained per the local retention policy.

## TRILUMINATE Pivotal CIP (Version F)

Defined as treatment in any inpatient unit or ward in the hospital for at least 24 hours, including emergency department stay for conditions such as coronary artery disease, acute myocardial infarction, hypertension, cardiac arrhythmias, cardiomegaly, pericardial effusion, atherosclerosis and peripheral vascular disease, not related to heart failure as defined.

### NON-CARDIOVASCULAR HOSPITALIZATION

Hospitalizations that are not heart failure or other cardiovascular hospitalizations, as defined above, will be categorized as non-cardiovascular hospitalizations.

### LIVER FAILURE

New onset liver failure is defined as elevated alanine aminotransferase (ALT) or aspartate aminotransferase (AST) greater than 15 times the ULN.

### MAJOR ADVERSE EVENT (MAE)

MAE is a composite of cardiovascular mortality, new onset renal failure, endocarditis requiring surgery, and non-elective cardiovascular surgery for TriClip™ device related adverse events occurring after the index procedure

### MAJOR BLEEDING

Major bleeding is defined as bleeding  $\geq$  Type 3 based on a modified Bleeding Academic Research Consortium (BARC) definition:

- Type 3
  - Type 3a
    - Overt bleeding plus hemoglobin drop of 3 to <5 g/dL\* (provided hemoglobin drop is related to bleed)
    - Any transfusion with overt bleeding
  - Type 3b
    - Overt bleeding plus hemoglobin drop  $\geq$ 5 g/dL\* (provided hemoglobin drop is related to bleed)
    - Cardiac tamponade

**TRILUMINATE Pivotal CIP**  
(Version F)

- Bleeding requiring surgical intervention for control (excluding dental/nasal/skin/hemorrhoid)
- Bleeding requiring intravenous vasoactive agents
- Type 3c
  - Intracranial hemorrhage (does not include microbleeds or hemorrhagic transformation, does include intraspinal)
  - Subcategories confirmed by autopsy or imaging or lumbar puncture
  - Intraocular bleed compromising vision
- Type 4: CV Surgery-related bleeding
  - Perioperative intracranial bleeding within 48 h
  - Reoperation after closure of sternotomy for the purpose of controlling bleeding
  - Transfusion of  $\geq 5$  U whole blood or packed red blood cells within a 48-h period†
  - Chest tube output  $\geq 2$ L within a 24-h period
- Type 5: Fatal bleeding
  - Type 5a
    - Probable fatal bleeding; no autopsy or imaging confirmation but clinically suspicious
  - Type 5b
    - Definite fatal bleeding; overt bleeding or autopsy or imaging confirmation

\*Corrected for transfusion (1 U packed red blood cells or 1 U whole blood=1 g/dL hemoglobin)

†Cell saver products are not counted

## MAJOR VASCULAR COMPLICATION

Any major complication, relating to, or affecting, the circulatory system as a result of the TriClip™ procedure, including new onset of any of the following:

- Hematoma at access site >6 cm.;
- Retroperitoneal hematoma;
- Arterio-venous fistula;
- Symptomatic peripheral ischemia/ nerve injury with clinical signs or symptoms lasting >24 hours;
- Vascular surgical repair at catheter access sites;
- Pulmonary embolism;
- Ipsilateral deep vein thrombus; or
- Access site-related infection requiring intravenous antibiotics and/or extended hospitalization.

## MELD SCORE

The Model for End-Stage Liver Disease, or MELD, is a scoring system for assessing the severity of chronic liver disease. The following parameters are used to determine MELD score: Creatinine level, Bilirubin level, INR (international normalized ratio), and serum sodium level. The score is calculated as follows:

Candidates who are at least 12 years old receive an initial MELD(i) score equal to:

$0.957 \times \text{Loge}(\text{creatinine mg/dL}) + 0.378 \times \text{Loge}(\text{bilirubin mg/dL}) + 1.120 \times \text{Loge}(\text{INR}) + 0.643$   
Laboratory values less than 1.0 will be set to 1.0 when calculating a candidate's MELD score.

Study Document No: ABT-CIP-10249

Study Name: TRILUMINATE Pivotal

**CONFIDENTIAL:** May not be reproduced outside of Abbott without written permission from Document Control. This is a quality record which will be retained per the local retention policy.

## TRILUMINATE Pivotal CIP (Version F)

The following candidates will receive a creatinine value of 4.0 mg/dL:

- Candidates with a creatinine value greater than 4.0 mg/dL
- Candidates who received two or more dialysis treatments within the prior 7 days
- Candidates who received 24 hours of continuous veno-venous hemodialysis (CVVHD) within the prior 7 days

The maximum MELD score is 40. The MELD score derived from this calculation will be rounded to the tenth decimal place and then multiplied by 10.

For candidates with an initial MELD score greater than 11, the MELD score is then re-calculated as follows:  $MELD = MELD_{(i)} + 1.32*(137-Na) - [0.033*MELD_{(i)}*(137-Na)]$  Sodium values less than 125 mmol/L will be set to 125, and values greater than 137 mmol/L will be set to 137.

### MODIFIED RANKIN SCALE SCORE DESCRIPTIONS

0. No symptoms at all
1. No significant disability despite symptoms; able to carry out all usual duties and activities
2. Slight disability; unable to carry out all previous activities, but able to look after own affairs without assistance
3. Moderate disability; requiring some help, but able to walk without assistance
4. Moderately severe disability; unable to walk without assistance and unable to attend to own bodily needs without assistance
5. Severe disability; bedridden, incontinent and requiring constant nursing care and attention
6. Dead

### MYOCARDIAL INFARCTION

Myocardial infarction (MI) classification and criteria for diagnosis is defined as follows:

#### Peri-procedural MI ( $\leq 72$ hours after TriClip™ procedure)

Mandatory: CK-MB (preferred)  $\geq 10x$  ULN within 72 hrs. post- TriClip™ procedure in patient with normal baseline CK-MB

OR

Mandatory: CK-MB  $\geq 5x$  ULN within 72 hrs. post- TriClip™ procedure in patient with normal baseline CK-MB *plus* new pathological Q-waves in  $\geq 2$  contiguous leads, or new LBBB

#### Post-surgery

Mandatory: CK-MB  $\geq 10x$  ULN (preferred) within 24 hrs. of cardiothoracic surgery *plus 1 of the following*:

- New pathological Q-waves in  $\geq 2$  contiguous leads or new persistent LBBB on ECG  $\geq 30$  min. and  $\leq 72$  hrs. post-CABG cardiothoracic surgery, or

**TRILUMINATE Pivotal CIP**  
(Version F)

- New substantial wall motion abnormalities by imaging except new septal or apical abnormalities.

**Spontaneous MI (>72 hours after TriClip™ procedure)**

Any one of the following criteria:

- Detection of rise and/or fall of cardiac biomarkers (CK-MB) with at least one value above the upper limits of normal (ULN), together with evidence of myocardial ischemia with at least one of the following:
  - ECG changes indicative of new ischemia [new ST-T changes or new left bundle branch block (LBBB)]
  - New pathological Q waves in at least two contiguous leads
  - Imaging evidence of new loss of viable myocardium or new wall motion abnormality
- Sudden, unexpected cardiac death, involving cardiac arrest, often with symptoms suggestive of myocardial ischemia, and accompanied by presumably new ST elevation, or new LBBB, and/or evidence of fresh thrombus by coronary angiography and/or at autopsy, but death occurring before blood samples could be obtained, or at a time before the appearance of cardiac biomarkers in the blood.
- Pathological findings of an acute myocardial infarction.

**NEW YORK HEART ASSOCIATION CLASSIFICATION (NYHA CLASS)**

Class I	Patients with cardiac disease but without resulting limitations of physical activity.
Class II	Patients with cardiac disease resulting in slight limitation of physical activity. Patients are comfortable at rest. Ordinary physical activity results in fatigue, palpitation, dyspnea, or anginal pain.
Class III	Patients with cardiac disease resulting in marked limitation of physical activity. Patients are comfortable at rest. Less than ordinary physical activity causes fatigue, palpitation dyspnea, or anginal pain.
Class IV	Patients with cardiac disease resulting in inability to carry on any physical activity without discomfort. Symptoms of cardiac insufficiency or of the anginal syndrome may be present even at rest. If any physical activity is undertaken, discomfort is increased.

**TRILUMINATE Pivotal CIP**  
(Version F)

**NON-ELECTIVE (i.e., URGENT or EMERGENT) CARDIOVASCULAR SURGERY FOR DEVICE RELATED EVENTS**

Cardiovascular surgical procedure performed for device related complication requiring surgery within 24 hours of onset of adverse event, including events found during scheduled follow-up. If non-urgent surgery was performed within 24 hours of the onset of the adverse event but was not required within this timeframe, it will not be considered “non-elective”. Examples of Device Related Complications that may lead to non-elective cardiovascular surgery include, myocardial perforation, Single Leaflet Device Attachment (confirmed by Echo Core Lab), embolization of the TriClip™ or TriClip™ System components, iatrogenic atrial septal defect, or the need for tricuspid valve replacement instead of repair due at least in part to the TriClip™ procedure or the presence of the TriClip™.

**OPTIMAL MEDICAL THERAPY OR OPTIMAL THERAPY**

For Tricuspid Regurgitation: Currently per ESC 2012 guidelines, the only medical therapy described is, “Diuretics reduce congestion. Specific therapy of the underlying disease is warranted.” Subjects should be on stable dose of diuretics for 30 days before the screening assessments (such as TTE/TEE). Stable dose is defined as no more than a 100% increase or a 50% decrease in dose.

For Mitral Regurgitation: Subjects with current or prior symptoms of heart failure and reduced LVEF should be on stable optimally uptitrated medical therapy recommended according to current guidelines (J Am Coll Cardiol. 2013 Jun 5. doi:pii: S0735-1097(13)02114-1.) as standard of care for heart failure therapy in the United States. This minimally includes an ACE-inhibitor (ACE-I) at stable doses for 30 days prior to subject enrollment in the trial, if tolerated, and a beta blocker (carvedilol, sustained release metoprolol succinate, or bisoprolol) for 90 days prior to subject enrollment in the trial, if tolerated, with a stable up-titrated dose for 30 days prior to subject enrollment in the trial. This also includes an Angiotensin II Receptor Blocker (ARB) at stable doses for 30 days prior to subject enrollment in the trial, if tolerated, when ACE-I is not tolerated. Stable is defined as no more than a 100% increase or a 50% decrease in dose.

If the subject is intolerant to ACE-I, ARB, or beta blockers, documented evidence must be available. In those intolerant to both ACE-I and ARB, combination therapy with hydralazine and oral nitrate should be considered. Therapeutic equivalence for ACE-I substitutions is allowed within the trial enrollment stability timelines. Aldosterone receptor antagonists [or mineralocorticoid receptor antagonists] are recommended in patients with NYHA class II-IV heart failure and who have LVEF of 35% or less, unless contraindicated, to reduce morbidity and mortality. Patients with NYHA class II should have a history of prior cardiovascular hospitalization or elevated plasma natriuretic peptide levels to be considered for aldosterone receptor antagonists. If aldosterone inhibitor therapy is to be administered, it must be initiated and optimized at least 30 days prior to trial enrollment. Stability criteria are the same as for other neurohormonal antagonists. Eplerenone requires dosage stability for 30 days prior to subject enrollment in the trial similar to the other agents. Diuretics may be used as necessary to keep the subject euvolemic. All heart failure therapeutics and dosages should be documented in the electronic case report forms.

Study Document No: ABT-CIP-10249

Study Name: TRILUMINATE Pivotal

**CONFIDENTIAL:** May not be reproduced outside of Abbott without written permission from Document Control. This is a quality record which will be retained per the local retention policy.

## **TRILUMINATE Pivotal CIP**

(Version F)

It is recognized that approximately two-thirds of patients with HF have underlying CAD (ischemic cardiomyopathy). Therefore, it is imperative that appropriate treatment for CAD be used, according to the ACC/AHA Guidelines for Heart Failure. Specific recommendations listed in those guidelines are listed as follows:

- Use of nitrates and beta blockers for the treatment of angina,
- Coronary revascularization according to recommended guidelines in patients who have both HF and angina,
- Patients with coronary artery disease and HF should be treated in accordance with recommended guidelines for chronic stable angina,
- Use of antiplatelet agents for prevention of MI and death in patients with HF who have underlying coronary artery disease

In addition, revascularization (i.e., percutaneous coronary intervention, etc.) should occur prior to subject enrollment in the trial as applicable.

### **PERIPHERAL EDEMA**

Accumulation of fluid causing swelling in tissues perfused by the peripheral vascular system, usually in the lower limbs

### **RENAL FAILURE**

For this trial, new onset renal failure is defined as new need for dialysis or a creatinine increasing to 3.5 mg/dL or greater

Note: Increase of creatinine less 1.0 mg/dL over baseline is NOT considered renal failure

### **SINGLE LEAFLET DEVICE ATTACHMENT (SLDA)**

Defined as unilateral TriClip™ detachment from one leaflet as assessed by the study site and confirmed by the ECL. Reasons for TriClip™ Detachment include leaflet tearing, TriClip™ unlocking, TriClip™ fracture or inadequate TriClip™ placement. Not included are any fractures or other failures of the TriClip™ that do not result in TriClip™ detachment from one or both leaflets.

### **STROKE/CEREBROVASCULAR ACCIDENT and TIA**

Cerebrovascular Accident (Stroke) is defined as an acute episode of focal or global neurological dysfunction caused by brain, spinal cord, or retinal vascular injury as a result of hemorrhage or infarction. Stroke may be classified as ischemic or hemorrhagic with appropriate sub-definitions or as undetermined if there is insufficient information to allow categorization as ischemic or hemorrhagic.

**TRILUMINATE Pivotal CIP**  
(Version F)

An entity closely related to ischemic stroke is transient ischemic attack (TIA). TIA is defined as a transient episode of focal neurological dysfunction caused by brain, spinal cord, or retinal ischemia, without acute infarction. The difference between TIA and ischemic stroke is the presence of infarction. In the absence of affirmative evidence confirming the presence or absence of infarction, a symptom duration of 24 hours will be used to distinguish TIA from ischemic stroke. By definition, TIA does not produce lasting disability.

The assessment of disability resulting from the stroke will be performed by the modified Rankin Scale (mRS). Assessment of the mRS is only required at scheduled visits through 24 months after onset of stroke, if stroke occurred. This approach will maximize the detection of new strokes, assist in ongoing evaluation of events previously determined to be TIAs, and provide an accepted and reliable indicator of the long-term impact of a given stroke. A disabling stroke is one that results (at 90 days after stroke onset) in an mRS score of 2 or more and in an increase of at least one mRS category from the individual's pre-stroke baseline. A non-disabling stroke is one that results (at 90 days after stroke onset) in an mRS score of less than 2 or that does not result in an increase of at least one mRS category from an individual's pre-stroke baseline.

Although imaging (typically, MRI for acute and chronic ischemia and haemorrhage, and CT for acute and chronic haemorrhage and chronic ischemia) is often used to supplement the clinical diagnosis of stroke, a diagnosis of stroke may be made on clinical grounds alone.

**Diagnostic criteria**

Acute episode of a focal or global neurological deficit with at least one of the following: change in level of consciousness, hemiplegia, hemiparesis, numbness or sensory loss affecting one side of the body, dysphasia or aphasia, hemianopia, amaurosis fugax, or other neurological signs or symptoms consistent with stroke

Stroke – Duration of a focal or global neurological deficit  $\geq 24$  h; OR  $< 24$  h if available neuroimaging documents a new hemorrhage or infarct; OR the neurological deficit results in death

TIA – Duration of a focal or global neurological deficit  $< 24$  h, any variable neuroimaging does not demonstrate a new hemorrhage or infarct

No other readily identifiable non-stroke cause for the clinical presentation (e.g. brain tumor, trauma, infection, hypoglycemia, peripheral lesion, pharmacological influences), to be determined by or in conjunction with designated neurologist\*

Confirmation of the diagnosis by at least one of the following:

- Neurologist or neurosurgical specialist
- Neuroimaging procedure (CT scan or brain MRI), but stroke may be diagnosed on clinical grounds alone

**TRILUMINATE Pivotal CIP**  
(Version F)

**Stroke classification**

Ischemic – An acute episode of focal cerebral, spinal, or retinal dysfunction caused by infarction of central nervous system tissue.

Hemorrhagic – An acute episode of focal or global cerebral or spinal dysfunction caused by intraparenchymal, intraventricular, or subarachnoid hemorrhage.

Undetermined – An acute episode where there is insufficient information to allow categorization as ischemic or hemorrhagic.

**Stroke definitions†**

Disabling stroke – a mRS score of 2 or more at 90 days and an increase of at least one mRS category from an individual's pre-stroke baseline

Non-disabling stroke – a mRS score of less than 2 at 90 days or one that does not result in an increase of at least one mRS category from an individual's pre-stroke baseline

\*Patients with non-focal global encephalopathy will not be reported as a stroke without unequivocal evidence of cerebral infarction based upon neuroimaging studies (CT scan or Brain MRI).

†Modified Rankin Scale assessments should be made by qualified individuals according to a certification process.

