## **6.5 Subject Withdrawal**

Each enrolled subject shall remain in the clinical investigation until completion of the required follow-up period; however, a subject's participation in any clinical investigation is voluntary and the subject has the right to withdraw at any time without penalty or loss of benefit. Conceivable reasons for discontinuation may include, but not be limited to, the following:

- Subject death
- Subject voluntary withdrawal
- Subject lost-to follow-up as described below

The Sponsor must be notified of the reason(s) for subject discontinuation. The site will provide this information to the Sponsor. Investigators must also report this to their respective IRB/EC as defined by their institution's procedure(s).

No additional follow-up will be required or data recorded from subjects once withdrawn from the clinical investigation, except for the status (deceased/alive).

However, if a subject withdraws from the investigation due to problems related to the safety or performance of the device under investigation, the investigator shall ask for the subject's permission to follow his/her status/condition outside of the clinical investigation.

In case of subject withdrawal, the site should make attempts to schedule the subject for a final clinical investigation visit. At this final follow-up visit, the subject will undergo the following assessments:

- 12-lead ECG
- Blood draw (Same as required for follow-up visits)
- Physical exam including vital signs (weight, heart rate and blood pressure)
- Echocardiogram – TTE
- Modified Rankin Scale (Assessment of mRS should be done only after onset of stroke; not required after 12 months)
- 6-Minute Walk Test (6MWT) – See **APPENDIX XIII** for 6 Minute Walk Test Guidelines
- Concomitant cardiovascular medications assessment
- NYHA Functional Class assessment
- KCCQ QoL questionnaire to be completed by the subject – must be administered by “blinded” study personnel. Note: To minimize bias and undue influence, the QoL questionnaires will be completed by the subject, unless the subject is unable to

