### **7.10.2 Follow-up for All Subjects**

Required clinical follow-up will be performed at the following intervals (based on treatment visit) for all subjects with TriClip™ procedure attempt, regardless of whether a TriClip™ was successfully implanted:

- Discharge post-TriClip™ procedure
- 30 days (-3/+14 days) follow-up visit (this visit must be conducted even if subject is in hospital)
- 6 months (180 days ± 28 days) follow up visit
- 1 year (365 days ± 28 days) follow up visit
- 18 months (545 days ± 28 days) follow up visit
- 2 years (730 days ± 28 days) follow up visit
- 3 years (1095 days ± 28 days) follow up visit
- 4 years (1460 days ± 28 days) follow up visit
- 5 years (1825 days ± 28 days) follow up visit

Follow-up visits will be calculated from the date of the Index Procedure (for subjects receiving the device) and the Treatment visit for subjects in the Control group. Follow-up assessments can be performed at any point in the window, and should be conducted, whenever possible, by the same individual who performed the baseline tests. The subject should be followed at the investigational site where the subject was enrolled and may be followed at another investigational site only with prior agreement from that site’s Investigator and from the Sponsor.

At the 30-day follow-up visit, the echocardiographer shall examine the integrity of the TriClip™. Subjects must continue to take baseline medications without change during follow-up, unless clinically (medically) necessary. If there are any cardiovascular medication changes (including dosage changes), these changes should be documented on the electronic case report form. In general, neurohormonal antagonists should not be changed. Subjects implanted with the

Study Document No: ABT-CIP-10249

Study Name: TRILUMINATE Pivotal

**CONFIDENTIAL:** May not be reproduced outside of Abbott without written permission from Document Control. This is a quality record which will be retained per the local retention policy.

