## TRILUMINATE Pivotal CIP (Version F)

TriClip™ must also be evaluated for device integrity. Required tests and procedures outlined below must be completed. Timing of specific tests will follow the Clinical Evaluation Schedule (**Table 1**) outlined below. These clinical assessments are standard assessments for most cardiac/structural heart interventional procedures and therefore should be administered per standard of care at each Institution. All visits and tests must be completed even if the subject is in hospital. Refer to the Schedule of Events table section 7.15 for timing of below listed tests.

- 12-lead ECG
- Blood draw
- Physical exam including vital signs (weight, heart rate and blood pressure)
- Echocardiogram – TTE at all follow-up visits
- Modified Rankin Scale (Required at visits occurring after onset of stroke)
- 6-Minute Walk Test (6MWT)– See **APPENDIX XIII** for 6 Minute Walk Test Guidelines
- Concomitant cardiovascular medications assessment
- NYHA Functional Class assessment
- KCCQ QoL and SF-36 questionnaires to be completed by the subject – must be administered by “blinded” study personnel. Note: To minimize bias and undue influence, the QoL questionnaires will be completed by the subject, unless the subject is unable to complete the questionnaire on their own (a note to file must be completed to document the inability of subject to complete the questionnaire)
- Assess and record adverse events
- Assess and record protocol deviations

All subjects should continue to be monitored and treated per applicable standards of care consistent with the subject’s condition. The site Principal Investigator should collaborate with the other site investigators as applicable in determining the treatment strategy for all subjects enrolled at their site. The electronic case report forms will document changes in treatment strategy (i.e. new use of CRT, PCI, tricuspid valve surgery, and/or mitral valve surgery) and who was involved with determining changes in treatment strategy. Subjects implanted with the Clip must be evaluated for device integrity.

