**7.15 Schedule of Events**

**Table 1: Clinical Evaluation Schedule**

CIP Activity	Screening	Baseline	Procedure	Discharge (>16hr post-procedure)	30 days (-3/+14 days)	6 Month (±28 days)	12, 18 months, 2-5 years (±28 days)
Informed Consent Process	X						
Demographics	X						
Physical Examination & Vital Signs	X	X	X b	X	X	X	X
Local Heart Team Evaluation	X						
Cardiovascular History	X						
Medical History	X						
Cardiovascular Medications	X	X	X	X	X	X	X
Echocardiogram	X (TTE and TEE)	X (TTE only) a	X (TEE only)	X (TTE Only)	X (TTE only)	X (TTE Only)	X e (TTE only)
RHC	X						
CT c		X c			X c		X c (1 year only)
MRI		X c			X c		
CBC with differentials and platelet count	X	X a		X	X	X	X
Gamma-GGT d , BNP or NT-proBNP, CK or CK-MB, BUN, serum creatinine, AST, ALT, INR (while on anticoagulation), Bilirubin, Serum Sodium	X	X a		X	X	X	X
KCCQ		X			X g	X g	X e, g
SF-36		X			X g		X (1 and 2 year only) g
6-Minute Walk		X				X g	X e, g
NYHA FC	X	X		X	X g	X g	X g
12-lead ECG	X	X	X b	X	X	X	X
Modified Rankin Scale f				X	X	X	X
Hospitalizations	X (prior 12 months)	X	X	X	X	X	X
Adverse Events/Deviation		X	X	X	X	X	X
Device Deficiency			X	X	X	X	X
Withdrawal		X	X	X	X	X	X

a If performed within 14 days of assessment for screening, then screening can be used for baseline.

b Must be performed within 24 hours prior to procedure (Device, Single-arm and Roll-in Group).

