# TRILUMINATE Pivotal CIP (Version F)

c Only required for subjects in the imaging sub study.

d Only required for sites with capability.

e Not required at 18 months.

f Only required at visit after onset of stroke, if stroke occurred.

g These assessments during these visits should be completed by blinded personnel

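### Stroke disability is defined by mRS 90 days after onset and its rise from a pre-stroke score, but the visit schedule provides for neither measurement

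*Protocol*

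**What the plan says.** The definition is in Protocol section 18 (Appendix II). The stroke table requires "a mRS score of 2 or more at 90 days and an increase of at least one mRS category from an individual's pre-stroke baseline" for a disabling stroke. The text above it fixes the clock: "A disabling stroke is one that results (at 90 days after stroke onset) in an mRS score of 2 or more". A stroke is non-disabling if either condition fails: a 90-day score below 2, or no rise of at least one category over the pre-stroke score. The same appendix asks that mRS be scored by qualified, certified individuals.

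Collection is described in several places:

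- **Table 1 (7.15)** marks mRS at Discharge, 30 days, 6 months, 12 and 18 months, and 2 to 5 years. Screening, Baseline and Procedure are blank. Footnote f reads "Only required at visit after onset of stroke, if stroke occurred".
- **6.2.1 (screening) and 7.3.1 (baseline)** list the assessments to be done, and mRS is not among them.
- **7.10.2 (follow-up)** asks for mRS only at visits after a stroke.
- **Appendix II** adds "Assessment of the mRS is only required at scheduled visits through 24 months after onset of stroke, if stroke occurred".
- **6.5 (final visit of a withdrawing subject)** says "Assessment of mRS should be done only after onset of stroke; not required after 12 months".

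Visits are counted from the index procedure, or from the Treatment visit in the Control group (7.10.2). The first is the "30 days (-3/+14 days) follow-up visit"; the next is at 180 ± 28 days.

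**The concern.** The severity definition needs two numbers for each stroke, and a site that follows the schedule exactly is not asked to obtain either at the required time. Section 11.9.4 has the Clinical Events Committee (CEC) adjudicate by the Protocol's definitions. To the extent that stroke is among its events, the disabling label would rest on scores that nobody was told to collect.

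The strokes of most interest for a transcatheter implant are those soon after the procedure, and these are the ones that the calendar misses most completely. At stake is the credibility of any statement on how severe strokes were in each arm, not a hypothesis test.

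**Working it through.** The plan states no figure to reproduce. The check is a comparison of lists, followed by calendar arithmetic.

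**Pre-stroke score.** Every list that could hold it (6.2.1, 7.3.1, Table 1, 7.10.2, 7.12.1, 6.5) either omits mRS or makes it conditional on a stroke. Scheduled collections: none.

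**Score 90 days after onset.** Inputs from 7.10.2, in days from the treatment visit:

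- 30-day window: 30 − 3 = 27 to 30 + 14 = 44
- 6-month window: 180 − 28 = 152 to 180 + 28 = 208
- later targets: 365, 545, 730, 1095, 1460 and 1825, each ±28

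The documents give no tolerance around 90 days. I assume ±14 and vary it below. Discharge has no fixed day, and visits triggered by tricuspid surgery, a further TriClip procedure or withdrawal are left out because they depend on another event.

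*Stroke on day s, with s from 0 to 30.* The target period runs from s + 76 to s + 104, so from day 76 (s = 0) to day 134 (s = 30). Days 76 to 134 lie wholly between day 44 and day 152, so coverage is 0%, even with full visit windows. The result does not hinge on ±14. For s = 30 the exact 90-day point is day 120, which is 152 − 120 = 32 days before the 6-month window opens. For s = 0 it is day 90, which is 90 − 44 = 46 days after the 30-day window closes. Any tolerance below 32 days leaves coverage at zero.

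*Strokes spread evenly over 5 years (assumption).* With tolerance t, a visit exactly on target day v serves onsets from v − 90 − t to v − 90 + t, a span of 2t days. If the visit may fall anywhere in v ± 28, the span is 2t + 56 days. The 30-day visit contributes nothing, because its span lies before day 0. The other seven spans do not overlap, so coverage is 7 × span / 1825.

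| Tolerance t | Visits on target | Full ±28-day windows |
|---|---|---|
| ±7 | 7 × 14 = 98; 5.4% | 7 × 70 = 490; 26.8% |
| ±14 | 7 × 28 = 196; 10.7% | 7 × 84 = 588; 32.2% |
| ±30 | 7 × 60 = 420; 23.0% | 7 × 116 = 812; 44.5% |

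The right-hand column is an upper limit: it counts a stroke as covered if the visit could be placed suitably within its window.

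**How long mRS continues.** Take a stroke on day 10. Table 1 and 7.10.2 set no end, so mRS is due at every visit to day 1825. Appendix II stops 24 months after onset, at about day 10 + 730 = 740, so the 3-, 4- and 5-year visits drop out. The 12-month limit in 6.5 applies only if the subject withdraws.

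**The case against.** A reader might infer that strokes cannot be classified at all. The documents do not support that.

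- A 90-day score below 2 makes a stroke non-disabling without any baseline.
- Death by day 90 is mRS 6 on the Protocol's scale, which exceeds any pre-stroke score.
- The schedule sets a minimum and does not forbid an extra assessment. Medical history is taken at screening, so a pre-stroke score could be reconstructed.
- The CEC charter and the case report forms are not available here and may contain a collection route.
- An early stroke is not left unassessed: mRS falls due at Discharge and the 30-day visit if the stroke precedes them, and at 6 months.

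All of this stands, and it limits the point to what the schedule provides for. It does not supply the pre-stroke score that a disabling label needs in a survivor.

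A reader might also see a three-way contradiction on duration. That is too strong. The 6.5 note concerns only the withdrawal visit, and the late columns of Table 1 are needed for late strokes: one at year 3 is due mRS at years 4 and 5 under Appendix II as well. What remains is a difference for early strokes and a withdrawal note that fits neither rule.

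Finally, stroke is not in the primary endpoint, the major adverse event composite, the powered secondary endpoints or the listed descriptive endpoints. SAP 3.2 summarises adjudicated events by count and percentage of subjects, without a severity split. The earlier TriClip study in Protocol 2.1.4, in which 91.8% had atrial fibrillation, reported no stroke through 6 months. Few events are likely, so the importance is modest.

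**Conclusion.** The point holds as a gap between a stated safety definition and the visit schedule. No pre-stroke mRS is scheduled, and no mRS is timed to 90 days after onset. From scheduled data, a survivor with mRS of 2 or more cannot be shown to have had a disabling stroke. For onset in the first 30 days no visit on the regular calendar can fall within 90 ± 14 days, and the same is true for any tolerance below 32 days. Over 5 years, about 11% to 32% of strokes could have a visit in that period, given the assumed ±14 days and evenly spread onset.

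No tested or listed endpoint, error rate or sample size changes. The effect is confined to adjudication and descriptive reporting of stroke severity. It is worth correcting because peri-procedural strokes are the ones left uncovered and the remedy is small.

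**What to change.** 1. For any subject with a stroke, have a certified assessor record the pre-stroke mRS retrospectively at the first contact after the stroke. A baseline mRS in every subject would avoid recall but is optional.
2. Add one mRS, by visit or telephone, at 90 days after onset, with a stated window such as ±14 days.
3. Give one rule for how long mRS continues after a stroke, and use it in Table 1, 7.10.2, Appendix II and the withdrawal-visit list in 6.5.

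The cost is one short extra contact for the few subjects with a stroke, plus a small amendment to the Protocol and case report forms. The retrospective score may carry recall error, so it should be flagged as retrospective in the data.
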